9.2.1. Criteria for elimination from analysis

If the participant meets one of the criteria mentioned below or ones listed in the Section 7.1.1 (contra-indication to subsequent vaccination) or 5.2.1 (medical conditions) or 5.2.2 (concomitant therapy), he/she may be eliminated from per protocol analysis.

In case of administration of any medication mentioned in Section 5.2.2 during the study, this will be considered as a protocol deviation and the participant may be eliminated from the PPS.

Participants may be eliminated from the PPS for immunogenicity if, during the study, they incur a condition that has the capability of altering their immune response (intercurrent medical condition) or are confirmed to have an alteration of their initial immune status. Refer to [Definition of Terms](#) for the definition of intercurrent medical conditions.

9.3. Statistical analyses

This section is a summary of the planned statistical analyses of the primary and secondary endpoints. Supportive analyses and demography summaries will be described in the SAP.

9.3.1. Primary endpoints/estimands analyses

The co-primary endpoints/estimands are described in Section 3. The primary analysis will be performed on the PPS.

MGI, i.e., the geometric mean of the within-participant ratios, of serum neutralizing titers against RSV-A and RSV-B post-Dose 2 (Visit 4) over post-Dose 1 (Visit 3) will be computed with their 95% CI in the RSV_IC_2 group.

CIs for MGI will be based on a back transformation of CI for the mean of the difference between log10-transformed values, assuming that log-transformed values are normally distributed with unknown variance.

Missing data will not be imputed.

9.3.2. Secondary endpoints/estimands analyses

Refer to Section 3 for the definition of secondary immunogenicity (humoral and CMI response) and safety endpoints. The immunogenicity analysis will be based on the PPS and safety analysis will be based on the ES.

For humoral immune response, the following analysis will be tabulated for each immunological assay (RSV-A and RSV-B neutralization titers):

- Percentage of participants above predefined threshold and GMT, with 95% CI, at pre-study intervention administration (Visit 1), Visit 2 (in a subset of participants), Visit 3, Visit 4, Visit 5, and Visit 6 in all groups.
- GMT ratio (RSV_HA group over RSV_IC group (pooled RSV_IC_1 and RSV_IC_2 group) with 95%CI, at Visit 2 (in a subset of participants) and Visit 3.
- GMT ratio (RSV_IC_2 group over RSV_IC_1 group) with 95% CI, at Visit 4, Visit 5, and Visit 6.
- GMT ratio (RSV_HA group over RSV_IC_1 group) with 95% CI, at Visit 4, Visit 5, and Visit 6.
- GMT ratio (RSV_HA group over RSV_IC_2 group) with 95%CI, at Visit 4, Visit 5, and Visit 6.
- MGI (RSV_IC group [pooled RSV_IC_1 and RSV_IC_2 group] and RSV_HA group) with 95% CI, at Visit 2 (in a subset of participants) over Visit 1, and at Visit 3 over Visit 1.

- MGI (RSV_IC_1, RSV_IC_2 and RSV_HA group) with 95% CI, at Visit 4, Visit 5 and Visit 6 over Visit 1.

The GMT ratios and their 95% CIs will be derived from an ANCOVA model on log10-transformed titers (details will be provided in the SAP).

The following analysis will be tabulated by group for CMI response in the CMI subset:

- Descriptive statistics (N, geometric mean, min, Q1, median, Q3, max) for the frequency of RSVPreF3-specific CD4+ and/or CD8+ T cells expressing at least 2 activation markers including at least one cytokine among CD40L, 4-1BB, IL-2, TNF- α , IFN- γ , IL-13, IL-17 at pre-study intervention administration (Visit 1), Visit 2, Visit 3, Visit 4, Visit 5, and Visit 6 in all groups.

Descriptive safety analysis by group will be summarized as follows:

- Percentage of participants reporting each solicited administration site event and solicited systemic event during a 7-day follow-up period (i.e., on the day of study intervention administration and 6 subsequent days) after each study intervention administration.
- Percentage of participants reporting unsolicited AEs during a 30-day follow-up period (i.e., on the day of study intervention administration and 29 subsequent days) after each study intervention administration by MedDRA Primary System Organ Class (SOC), High Level Term (HLT) and Preferred Term (PT).
- Percentage of participants reporting SAEs from study intervention administration (Day 1) up to study end (Visit 6) by MedDRA Primary SOC, HLT and PT.
- Percentage of participants reporting pIMDs from study intervention administration (Day 1) up to study end (Visit 6) by MedDRA Primary SOC, HLT and PT.
- Percentage of participants reporting SAEs related to study intervention administration from study intervention administration (Day 1) up to study end (Visit 6) by MedDRA Primary SOC, HLT and PT.
- Percentage of participants reporting pIMDs related to study intervention administration from study intervention administration (Day 1) up to study end (Visit 6) by MedDRA Primary SOC, HLT and PT.
- Percentage of participants reporting fatal SAEs from study intervention administration (Day 1) up to study end (Visit 6) by MedDRA Primary SOC, HLT and PT.
- Percentage of participants reporting AESIs (specific to renal and lung SOT patients) from study intervention administration (Day 1) up to study end (Visit 6) by MedDRA Primary SOC, HLT and PT.

- Percentage of participants reporting demyelinating disorder during a 30-day follow-up period (i.e., on the day of study intervention administration and 29 subsequent days) after each study intervention administration by MedDRA Primary SOC, HLT and PT.
- Percentage of participants reporting demyelinating disorder SAE from study intervention administration (Day 1) up to study end (Visit 6) by MedDRA Primary SOC, HLT and PT.

Exact 95% CIs around percentages will be computed using the method of Clopper and Pearson [[Clopper](#), 1934].

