Amendment 1 GER, ITA, SPN-1	04 September 2023
Original Protocol	25 April 2023

Type of Protocol Amendment	Numbering	Type of Changes
Global	Amendment 2 Final	New changes to allow the inclusion of lung or renal transplant patients as of 18 YoA and above
Country-specific	Amendment 1 GER, ITA, SPN-1 Final	New changes to address health authority feedback

Amendment 2 (11 Oct 2023)

This amendment is considered substantial based on the criteria defined in EU Clinical Trial Regulation No 536/2014 of the European Parliament and the Council of the European Union because it significantly impacts the scientific value of the study.

Overall rationale for the current Amendment:

To allow the inclusion of renal and lung solid organ transplant patients as of 18 years of age (YoA) and above. Renal and lung transplant recipient patients 18 YoA and above are at high risk of RSV-related LRTD, due to the life-long immunosuppressive therapy received for allograft rejection prevention regardless of their age [Dropulic, 2016; Fishman, 1998; Reichenberger, 2001].

Because of the safety signal of preterm birth observed in the RSV MAT-009 study, the initial RSV OA=ADJ-023 study protocol allowed only for the inclusion of participants as of 50 YoA (refer to Section 2.3.1).

Further evaluation of the preterm birth signal based on different analyses of the RSV MAT-009 study data, research on plausible biological mechanisms and recommendations by external experts led to the following conclusions:

- There is an identified risk for preterm birth in pregnant women vaccinated during the late second and third trimester with the RSV MAT vaccine candidate (refer to Section 2.3.1) and therefore pregnant women should be excluded from participation in the current study.

- The biological mechanism behind the identified risk of preterm birth in pregnant women who received the RSV MAT vaccine candidate is not known. Nevertheless, there is no theoretical mechanism to suggest a risk to future pregnancy for women vaccinated prior to pregnancy.

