- Precautionary measures to mitigate the risk of exposure to the RSVPreF3 OA vaccine at any time during pregnancy, such as not enrolling pregnant individuals, pregnancy testing before each administration of the study vaccine and adequate contraception for at least 1 month before the study intervention administration until the study end are included in the inclusion criteria in this study. (Refer to Section 10.4.1 for definitions of women of childbearing potential, menopause and Section 10.4.2 on adequate contraception).

Given the high observed efficacy of the RSVPreF3 OA vaccine in clinical studies in individuals 60 YoA and older, and taking into account the precautionary measures to be implemented for this study and the unmet medical need in the renal and lung solid organ transplant patient population as of 18 YoA, the anticipated benefit-risk of the RSVPreF3 OA vaccine supports the continued clinical development in less than 50-year-old non-pregnant adults at increased risk, especially the immunocompromised (IC) population.

Since the burden of RSV-related LRTD in healthy adults 18-49 YoA is low, the age range for the RSV_HA group was not adjusted.

List of main changes in the protocol and their rationale:

Section # and title	Description of change	Brief rationale
Title page 1.1 Synopsis 1.2 Schema, Figure 1 2.1 Study rationale 4 Study design 5.1 Inclusion Criteria 6.3.2 Randomization to study intervention 9.5 Pre-dose sample determination	Inclusion of adults ≥ 18 YoA in the IC population (participants with lung or renal transplant).	To include at risk population as of 18 YoA and improve the feasibility of recruitment of IC population.
2.1 Study rationale	Added market approval information for RSV OA vaccine	New information.
2.2 Background	Updated information on BoD of RSV in transplant patients.	Correction.
2.3 Benefit/risk assessment	Updated risk information for study vaccine in adults < 60 YoA.	Consistency update for risk information in population < 60 YoA, as the age was lowered to include ≥ 18 YoA and above.

Section # and title	Description of change	Brief rationale
	Correction and clarifications provided for the mitigation strategy for potential risks.	
3 Objectives endpoints and estimands 9.3.2 Secondary endpoints/estimands analyses	Secondary immunogenicity endpoints and their estimands analyses were added.	Added based on health authority feedback from Korea.

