4.2. Scientific rationale for study design

RSV is associated with serious illness in OA and high-risk adults, including those who are immunocompromised that may lead to increased risk of RSV-LRTD. The efficacy of a single dose of the RSVPreF3 OA investigational vaccine in the prevention of RSV-LRTD in OA ≥ 60 YoA has been shown in the Phase 3 clinical study RSV OA=ADJ-006 (refer to IB).

Since the immune response in IC patients is often lower compared to healthy persons, the current study is designed as a Phase 2, open-label study to evaluate the immune response, safety, and reactogenicity of 1 versus 2 doses of RSVPreF3 OA investigational vaccine in

an IC population (renal and lung SOT patients) ≥ 18 YoA and additionally comparing it to 1 dose in healthy participants ≥ 50 YoA.

The inclusion of the 1-dose group in the SOT patient groups will provide more robust information and will help to make an informed decision on the need to use 1 dose versus 2 doses by comparing the immune response (in terms of GMT ratios in neutralization titers against RSV-A and RSV-B, as well as cell-mediated immunity) in the 1-dose group at Visit 3 and Visit 4 with the immune response in the 2-dose group at Visit 4.

In addition, a comparison on humoral and cell-mediated immunity at all timepoints up to 12 months post-last dose (including Month 6 and Month 12) between both groups of SOT patients as well as comparison to healthy participants will provide important information on waning of the immune response. In this study, the inclusion of a group of healthy adults ≥ 50 YoA will help to better elucidate the potential differences in immunogenicity and safety in the SOT patient groups versus healthy participants as of 50 YoA. Having head-to-head comparison with the healthy group will aid in the characterization of the immune response (both humoral and cell-mediated) of the IC population. Specifically for RSV, it is important that the healthy group is included in the same study since the primed status of the healthy adults and therefore the immune response to the vaccine, might differ between studies, as RSV seasonality can be different across countries/regions and years. Moreover, a head-to-head comparison with the healthy participants group will also enable further characterization of the reactogenicity of RSVPreF3 OA vaccine in IC population.

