5.1.2. Specific inclusion criteria for renal/lung transplant patients

- A male or female participant, ≥ 18 YoA at the time of signing the Informed consent form (ICF) or Informed assent form (IAF).
- Written informed assent obtained from the participant (participant must be able to understand the informed assent) if he/she is less than legal age of consent*, or written informed consent obtained from the participant if the participant has achieved legal age of consent.

**The legal age of consent is determined according to local regulations in each participating country. Assent must be obtained from the minor participant in addition to the consent provided by the participants' parent(s)/LAR(s) when a minor can assent to participate in a study. If the legal age is achieved during the conduct of the study, an additional written informed consent from the participant should be obtained at that time.*

- Participant who has received an ABO compatible allogeneic renal or lung transplant (allograft) more than 12 months (365 days) prior to the first study intervention administration.
- Participant receiving maintenance immunosuppressive therapy for the prevention of allograft rejection.

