5.1.5. Specific inclusion criteria for healthy participants

- A male or female, ≥ 50 YoA at the time of signing the ICF.
- Healthy participants as established by medical history and clinical examination before entering the study.

- Participants who are medically stable in the opinion of the investigator at the time of first study intervention administration.
- Participants with chronic stable medical conditions with or without specific treatment, such as diabetes mellitus, hypertension, or cardiac disease, are allowed to participate in this study if considered by the investigator as medically stable.

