8.1. Administrative and baseline procedures

8.1.1. Collection of demographic data

Record demographic data such as year of birth, age at the time of study intervention administration, sex, race*, and ethnicity* in the participant's eCRF.

Collection of sex, race and ethnicity data is necessary to assess and monitor the diversity of the trial participants, and to determine if the trial participants are truly representative of the impacted population.

*Differences in the safety and efficacy of certain medical products, including vaccines [Haralambieva, 2013; Pérez-Losada, 2009; Kollmann, 2013] have been observed in racially and ethnically distinct subgroups. These differences may be attributable to intrinsic factors (e.g., genetics, metabolism, elimination), extrinsic factors (e.g., diet, environmental exposure, sociocultural issues), or interactions between these factors. Therefore, both geographic ancestry (race) and ethnicity will be collected for all study participants.

Age is collected to stratify the population and determine the impact of the study intervention by age.

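### Since Amendment 2 the HA/IC GMT ratios compare transplant recipients from age 18 with healthy adults from age 50, so they mix age with transplant status; ratios for recipients aged 50 and older should be prespecified alongside them

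*Protocol*

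**What the plan says.** **Age limits.** Section 5.1.2 admits transplant patients as "A male or female participant, ≥ 18 YoA at the time of signing the Informed consent form", with no upper limit. Section 5.1.5 admits healthy participants as "A male or female, ≥ 50 YoA at the time of signing the ICF". Sections 4.1, 6.3.3 and 9.5 set healthy-group quotas of 30% aged 50–59, 30% aged 60–69, 20% aged 70 or over and 20% free across those categories, so none is below 50.

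**How the gap arose.** The Amendment 2 rationale says that the initial "study protocol allowed only for the inclusion of participants as of 50 YoA". It lowers the limit for transplant patients and explains the healthy group thus: "Since the burden of RSV-related LRTD in healthy adults 18-49 YoA is low, the age range for the RSV_HA group was not adjusted".

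**Allocation.** Transplant patients are randomised 1:1 to one or two doses, stratified by transplant type and CMI subset, not by age (Sections 6.3.2 and 6.3.3). Healthy participants are assigned to their group, not randomised.

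**Analysis.** Section 9.3.2 plans the "GMT ratio (RSV_HA group over RSV_IC group (pooled RSV_IC_1 and RSV_IC_2 group) with 95%CI" at Visits 2 and 3, and healthy over each transplant arm at Visits 4, 5 and 6. All come from an ANCOVA on log10 titres, with details left to the SAP. Section 4.2 gives the purpose as clarifying "differences in immunogenicity and safety in the SOT patient groups versus healthy participants as of 50 YoA". Section 8.1.1 adds: "Age is collected to stratify the population and determine the impact of the study intervention by age".

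**The concern.** While everyone had to be at least 50, the two sides of the HA/IC ratio shared an age floor. That floor now holds on one side only. The reason given, low disease burden in healthy adults aged 18 to 49, explains why younger controls were not enrolled. It does not address whether healthy and transplant titres remain comparable.

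If titre response depends on age, an all-ages ratio reflects both transplant status and the younger age mix of the transplant arms. If younger recipients respond better than older ones, a real transplant deficit is pulled toward 1. If they respond worse, it is exaggerated. The protocol gives no information on which applies.

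Putting age in the ANCOVA helps where both groups have data, from 50 upward. Below 50 there is no healthy participant, so a healthy value at those ages would rest on extending the age relation beyond the observed healthy range. The trial cannot check that extension.

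**Working it through.** **Inputs from the protocol (Sections 9.5 and 9.5.1).** SD of log10 titre 0.45 (healthy) and 0.50 (IC); one-sided alpha 2.5%; power 80%; 100 evaluable per group after 20% attrition from 125 (125 × 0.80 = 100). Stated detectable ratios: 1.55 for one IC arm versus healthy, 1.45 for pooled IC versus healthy.

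**Step 1: reproduce the plan's figures.** Two-sample t-test with unequal variances (noncentral t, Satterthwaite df), noncentrality log10(ratio)/SE, where SE = √(0.45²/n_HA + 0.50²/n_IC).

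- 100 versus 100: SE = √(0.002025 + 0.002500) = 0.0673; detectable ratio 1.547; power at 1.55 is 80.4%.
- 100 versus 200: SE = √(0.002025 + 0.001250) = 0.0572; detectable ratio 1.449; power at 1.45 is 80.2%.

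Both stated figures are correct.

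**Step 2: how the age mix enters an unadjusted ratio.** Let q be the share of IC participants under 50, and g the GMT of recipients under 50 divided by the GMT of recipients aged 50 and older. On the log scale the IC mean is a weighted average, so GMT(all IC) = GMT(IC 50 and older) × g^q, and

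observed HA/IC = (HA/IC among those 50 and older) ÷ g^q.

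The protocol gives neither q nor g. The values below are assumptions chosen to show the range in both directions.

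| q | g | ratio of 1.45 (pooled) reads as | ratio of 1.55 (one arm) reads as |
|---|---|---|---|
| 0.25 | 0.8 | 1.53 | 1.64 |
| 0.25 | 1.0 | 1.45 | 1.55 |
| 0.25 | 1.25 | 1.37 | 1.47 |
| 0.25 | 1.5 | 1.31 | 1.40 |
| 0.50 | 0.8 | 1.62 | 1.73 |
| 0.50 | 1.0 | 1.45 | 1.55 |
| 0.50 | 1.25 | 1.30 | 1.39 |
| 0.50 | 1.5 | 1.18 | 1.27 |

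For example, 1.45 ÷ 1.5^0.25 = 1.45 ÷ 1.107 = 1.31, and 1.45 ÷ 0.8^0.5 = 1.45 ÷ 0.894 = 1.62. With g = 1 nothing changes.

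**Step 3: the price of restricting to IC aged 50 and older.** Same test, with n_IC multiplied by (1 − q).

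| q (assumed) | pooled IC n | detectable ratio | one-arm n | detectable ratio |
|---|---|---|---|---|
| 0 | 200 | 1.45 | 100 | 1.55 |
| 0.20 | 160 | 1.47 | 80 | 1.59 |
| 0.25 | 150 | 1.48 | 75 | 1.61 |
| 0.50 | 100 | 1.55 | 50 | 1.73 |

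**Step 4: Visit 2.** Only the CMI subset is sampled, about 38 per group (Section 6.3.4). Pooled IC is about 76 before attrition. With 20 to 50% under 50, that leaves about 61 (76 × 0.8) down to 38 (76 × 0.5), which suits description only.

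**Step 5: what is untouched.** The primary MGI is a within-participant ratio in the two-dose arm (Section 9.3.1). The IC_2/IC_1 ratio compares randomised arms with the same age rule. Neither uses the healthy group.

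**The case against.** The strongest reply is that this is SAP content. Section 9.3 describes itself as a summary, the ANCOVA details are deferred, and Section 8.1.1 signals age-based analysis. That stands as far as the age covariate goes: its absence from the protocol is not a fault. It does not dispose of the point, because Section 9.3.2 defines the HA/IC ratios on whole groups and no covariate creates healthy participants under 50.

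A second reply is that Section 4.2, like the title, names its reference as healthy participants from 50 years. This is right. A reader might infer that the protocol presents the ratio as an isolated effect of transplantation. It makes no such claim; the ratio is computable as described, and the risk lies in how it will be read.

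Other stronger readings also go too far:

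- That the ratio will understate the transplant deficit. This needs younger recipients to respond better, and the protocol gives no age effect. With g = 0.8 the deficit is overstated.
- That the two groups have no common age range. They overlap from 50 upward, which is what makes the remedy possible.
- That Amendment 2 left the analysis unchanged. Its list of changes includes Section 9.3.2, where secondary analyses were added.

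Finally, the comparison is secondary in a descriptive study (Section 9.5.1), and the question of one versus two doses is answered within the transplant arms. This limits the weight of the point.

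**Conclusion.** The point holds in a limited form. The all-ages HA/IC GMT ratios mix age with transplant status because the two sides have had different age floors since Amendment 2, and the stated reason for that difference does not bear on comparability. Neither the direction nor the size of the bias can be determined from the protocol. The values of q and g above are assumptions, and the formula describes an unadjusted ratio; an ANCOVA with age would change the numbers but would still have no healthy data below 50. If few recipients under 50 enrol, or age has little effect on titre, the bias is small. The sample-size calculations are correct. This is a cheap improvement, not a flaw in the primary analysis.

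**What to change.** In Section 9.3.2:

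- Keep the all-ages HA/IC ratios as the planned secondary endpoints.
- Prespecify the same ratios restricted to IC participants aged 50 and older, with age in the ANCOVA: pooled IC at Visits 2 and 3, by arm at Visits 4, 5 and 6. Mark Visit 2 as descriptive only, because it is confined to the CMI subset.
- State that any conclusion about transplant recipients versus healthy adults is read from this age-overlapping comparison.
- Summarise IC participants aged 18 to 49 descriptively.

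The cost is protocol wording and additional tables. Age is already collected, so no new participants, visits or samples are needed. The downside is the loss of precision in Step 3, which is modest for the pooled ratio but more noticeable for a single arm if half the recipients are under 50. Fixing the restriction in advance also avoids choosing it after the results of an open-label study are known.
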